HCP should refer to the HCP material and checklist to inform patient about specificities of the pen use.

Q6. According to your knowledge what should be the important information to be indicated in the prescription for Suliqua? (you can select more than one answer)

	Prescription	
1	Number of dose steps to be injected	()
2	Strength of pen	()
3	Name of product	()
4	Associated dose range /strength	()

Data: multiple punch

Answer: mandatory: 1,3,4;

Key message

The prescription should mention which pre-filled pen type you need (the SULIQUA [100 units/mL + 50 micrograms / mL] pen or the SULIQUA [100 units/mL + 33micrograms / mL] pen) and the number of dose steps to be injected.

Q7. According to your knowledge, which of the following Suliqua safety messages should be communicated to patients treated with Suliqua ? (you can select more than one answer)

	Safety messages	
1	Patients may experience side effects and should talk to their doctors or pharmacists	()
2	Patients may develop osteosarcoma and should be monitored for bone pain and swelling	()
3	Medication errors are the most common cause of adverse events and patients should ask, if needed, clarifications on how to use their pen and on how many dose steps they require	()

4	Patients may experience dysglycemia and should measure their blood sugar more frequently in the weeks after the shift to Suliqua	()
---	--	-----

Data: multiple punch

Answer: Option 2 is wrong

Key message:

HCPs should explain that the patient should anticipate dysglycemia and potential adverse reactions.

Q8. According to your experience, which of the following are the most relevant sources of information that should guarantee appropriate use of Suliqua by patients? (you can select more than one answer)

	Source of information	
1	Patient guide	()
2	Patient leaflet and instructions for use accompanying the pen	()
3	Explanations from prescribing physician	()
4	Explanations from delivering pharmacist	()
5	Explanations from a nurse	()
6	Other (ie: Patient group experience, internet, ..)	()

Data: multiple punch

Q9 and Q10 for prescribers [D2a=1 or 2 or 4 or 5]

Q9. How many prescriptions for Suliqua have you been queried about or have been returned for clarification by dispensers / pharmacists in the last 3 months?

1	None (0)	()
2	1-5	()
3	6-10	()
4	11-20	()
5	>20	()

Data: Single punch

Q10 How many prescriptions for Suliqua have you been queried about or have you been asked for clarification by patients in the last 3 months?

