1	None (0)	()
2	1-5	()
3	6-10	()

4	11-20	()
5	>20	()

Data: Single punch

Q9 and Q10 for dispensers [D2a=3]

Q9 How many prescriptions for Suliqua have you been queried about or returned for clarification by the prescriber in the last 3 months?

1	None (0)	()
2	1-5	()
3	6-10	()
4	11-20	()
5	>20	()

Data: Single punch

Q10 How many prescriptions for Suliqua have you been queried about for clarification by patients in the last 3 months?

1	None (0)	()
2	1-5	()
3	6-10	()
4	11-20	()
5	>20	()

Data: Single punch

Another survey will be conducted to assess the knowledge and understanding of the key safety messages in the Patient Guide among patients treated with Suliqua. Would you like to help us, by giving the survey questionnaire to your patients? They will then complete an online/paper questionnaire anonymously without your involvement. You will be paid: **XX € / completed patient/caregiver questionnaire. IQVIA will re-contact you in order to make the necessary arrangements for patient survey distribution.**

1. Yes, I would like to distribute the patient survey among my patients. I agree to be contacted again for this purpose.
2. No

Data: Single punch

If yes, display :

1. I would like to be contacted by IQVIA using the default contact information
2. I would like to provide different contact information

Data: Single punch

If item 2 selected then show:

Please confirm your details:

YOUR NAME:	
E-MAIL ADDRESS:	
ADDRESS:	

Note:

Blue is for data and will not appear in questionnaire,

Green is for internal use and will not appear in questionnaire,

Black will be in the questionnaire.

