- Pharmacists are encouraged to check that patients and caretakers are able to read the strength of SULIQUA™, the dose range of the pre-filled pen, and the dose pointer of the pre-filled pen before dispensing SULIQUA™.
- Pharmacists should also check that patients have been trained on how to use the pen.
- Pharmacists should clarify with the prescriber any incomplete prescription.

While both pens are available for use, the individual needs of your country may lead you to hear about only one pen from your sales representative.

A CHECKLIST FOR HEALTHCARE PROFESSIONALS

EXPLAIN TO YOUR PATIENT

- You are prescribing a number of dose steps that corresponds to a set number of Units of insulin glargine 100 U/mL plus a corresponding amount of lixisenatide.
- For SULIQUA™, one dose step always contains one Unit of insulin glargine 100 U/mL, regardless of the SULIQUA™ pre-filled pen being used (the SULIQUA™ [10-40] pen or the SULIQUA™ [30-60] pen).
- The dose pointer shows the number of dose steps to be injected.
- If your patient has been transferred from a different pre-filled pen device, highlight the differences in design between the two devices (focus on color differentiation and warning statements on packaging/label).
- Explain what the patient should anticipate regarding dysglycaemia and potential adverse reactions. For a complete list of adverse events, please refer to the SULIQUA™ Summary of Product Characteristics.
- Patients who are blind or have poor vision must be instructed to always get assistance from another person who has good vision and is trained in the SULIQUA™ SoloStar® pen device.
- Instruct your patients to always use a new needle before each use and to never use a syringe to remove the solution from the pen to avoid dosing errors and potential overdose.
- Recommend that your patients read the patient guide and the patient information leaflet carefully, as well as the instructions for use leaflet provided in the SULIQUA™ SoloStar® packaging.
- Tell patients to closely monitor their blood sugar levels when starting SULIQUA™, which contains insulin glargine 100 U/mL and a non-insulin active substance (lixisenatide).

IMPORTANT SAFETY INFORMATION

SULIQUA™ is supplied in a pre-filled pen and must only be used with this device; healthcare professionals must never use a syringe to withdraw SULIQUA™ from a pre-filled pen or dosing errors and serious harm can result.

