Annex 5 Patient Guide

GUIDE FOR PATIENTS AND/OR CAREGIVERS

THIS CARD IS PROVIDED ONLY AS A GUIDE. BEFORE USING SULIQUA™, YOU MUST BE TRAINED ON HOW TO USE THE SULIQUA™ SOLOSTAR® PEN BY YOUR HEALTHCARE PROFESSIONAL, AND YOU MUST CAREFULLY READ THE PATIENT LEAFLET AND THE INSTRUCTIONS FOR USE ACCOMPANYING THE PEN.

Keep this card. You may need to refer to it again. Write your name on this card: _____

SULIQUA™ 10-40 PEN

SULIQUA™ 100 UNITS/mL + 50 MICROGRAMS/mL
 SOLUTION FOR INJECTION IN A PRE-FILLED PEN

SULIQUA™ 30-60 PEN

SULIQUA™ 100 UNITS/mL + 33 MICROGRAMS/mL
 SOLUTION FOR INJECTION IN A PRE-FILLED PEN

SULIQUA™ is available in 2 pre-filled pens containing 2 different strengths of lixisenatide, and different dose ranges of insulin glargine 100 U/mL. Your healthcare professional has prescribed the pen that is right for your insulin needs.

SULIQUA™ pre-filled pens simultaneously deliver insulin glargine and lixisenatide in a single, once-daily injection.

- Both pre-filled pens contain insulin glargine in a strength of 100 Units/mL.
- The SULIQUA™ (10-40) pen allows a daily injection of doses between 10 and 40 dose steps (strength: insulin glargine 100 Units/mL and lixisenatide 50 mcg/mL; dose range: 10 to 40 Units of insulin glargine in combination with 5 to 20 mcg lixisenatide). This pen is peach colored with an orange injection button.
- The SULIQUA™ (30-60) pen allows a daily injection of doses between 30 and 60 dose steps (strength: insulin glargine 100 Units/mL and lixisenatide 33 mcg/mL; dose range: 30 to 60 Units insulin glargine in combination with 10 to 20 mcg lixisenatide). This pen is olive colored with a brown injection button.
- The prescription should mention which pre-filled pen type you need (the SULIQUA™ [10-40] pen or the SULIQUA™ [30-60] pen) and the number of dose steps to be injected.
- Your Pharmacist should clarify with your prescriber any incomplete prescription.
- One dose step contains one unit of insulin glargine 100 U/mL plus a corresponding amount of lixisenatide. Before you use SULIQUA™, be clear on how many dose steps you require. Your healthcare professional provided you with this information.
- The dose pointer of the pre-filled pen device shows the number of dose steps to be injected.

GUIDE FOR PATIENTS AND/OR CAREGIVERS

TAKE NOTE:

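### Dispenser Q9 is worded in a reversed or ambiguous direction, so pharmacists' answers cannot be read as a count of unclear prescriptions seen at dispensing

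*Protocol*

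**What the plan says.** Annex 2 of the protocol (HCP survey questionnaire) has two versions of Q9 with the same response bands, from none to more than 20.

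- **Pharmacists (D2a = 3)** are asked: "How many prescriptions for Suliqua have you been queried about or returned for clarification by the prescriber in the last 3 months".
- **Prescribers (D2a = 1, 2, 4 or 5)** are asked how many prescriptions they "have you been queried about or have been returned for clarification by dispensers / pharmacists in the last 3 months".

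The educational materials give one direction for this contact. The HCP guide (Annex 4, pharmacist guidance) says: "Pharmacists should clarify with the prescriber any incomplete prescription". The patient guide (Annex 5) says: "Your Pharmacist should clarify with your prescriber any incomplete prescription".

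The only other event count put to dispensers after screening is their Q10, which concerns patients: "How many prescriptions for Suliqua have you been queried about for clarification by patients in the last 3 months".

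Section 9.7.1 makes the distribution of answers to each question part of the primary analysis. Its mock Table 4 reports by specialty and country, with unweighted and weighted overall rows.

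**The concern.** The pharmacist version looks like the prescriber version with the passive kept and the other party swapped in. That turns the event round. Someone who dispenses receives prescriptions and sends back those that are unclear; the prescriber does not normally send a prescription back to the pharmacy.

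Section 7.2 says the guides were required because of possible medication errors by prescribers, dispensers and patients. Pharmacists' own experience of unclear SULIQUA prescriptions is direct descriptive evidence on the dispensing step, and this is the only pharmacist item that could supply it. If the answers cluster at *None (0)* because of the wording, a reader of the report could take them as a sign that prescriptions reach pharmacies complete.

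**Working it through.** There is no figure in the plan to reproduce and no sample-size or power formula applies. The check compares the texts.

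**Step 1: direction of contact in each source**

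| Source | Who raises the query | Who receives it |
|---|---|---|
| HCP guide, Annex 4 | Pharmacist | Prescriber |
| Patient guide, Annex 5 | Pharmacist | Prescriber |
| Prescriber Q9, Annex 2 | Pharmacist/dispenser | Prescriber |
| Dispenser Q9, limb 1 (queried) | Prescriber | Pharmacist |
| Dispenser Q9, limb 2 (returned) | Unclear | Unclear |

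Three sources agree. Limb 1 of dispenser Q9 is the reverse.

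**Step 2: the two readings of limb 2.** Read as a passive governed by the same auxiliary, it means that the prescriber returned the prescription. Read as an active verb, it means that the pharmacist returned it so that the prescriber could clarify it, which is the guides' flow. The prescriber version repeats the auxiliary before the second verb ("have been returned for clarification by dispensers / pharmacists in the last 3 months"); the pharmacist version does not, so the active reading is open.

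**Step 3: what each reading counts.** For one pharmacist over 3 months, let *a* be prescriptions the pharmacist queried with the prescriber without returning them, *b* prescriptions the pharmacist returned, *c* prescriptions the prescriber queried with the pharmacist, and *d* prescriptions the prescriber returned to the pharmacist.

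- Count wanted: *a* + *b*
- Fully passive reading: *c* + *d*
- Limb 2 read as active: *c* + *b*
- Respondent guesses the intent: *a* + *b*

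Neither literal reading counts *a*, and only one counts *b*. A pharmacist who returned 6-10 prescriptions and was never contacted by a prescriber ticks *None (0)* on the fully passive reading and 6-10 on the active one. The recorded answer does not show which reading was used.

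**Step 4: is the count available elsewhere?** From dispensers, no: Q10 covers only queries from patients. From prescribers, yes: their Q9 covers queries and returns by pharmacists over the same 3 months in the same bands. It comes from different respondents and is routed to D2a = 1, 2, 4 and 5, so geriatrics (D2a = 6) receives neither version.

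**Step 5: does a decision depend on it?** Section 9.7.1 builds the HCP success factors from Q1; from Q3-Q4 with Q7; and from Q2a-b with Q5-Q6. Q9 is in none of them, so the rule of at least 2 of 3 proportions at or above 80% is unaffected.

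**The case against.** The case for leaving the item alone has four parts.

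- **The event is still measured.** Prescriber Q9 asks about it with the same recall period and bands. This stands. A reader might infer that returned prescriptions cannot be measured at all in this survey; the documents do not support that. What is lost is an interpretable count from the dispensers themselves.
- **The wording is ambiguous rather than simply reversed.** This stands for the second limb. A reader might also infer that the share of pharmacists answering above *None (0)* would be about 0% whatever the true rate. That needs every pharmacist to take the fully passive reading and prescribers never to contact pharmacists, and the protocol states neither. The ambiguity does not rescue the item, because a mix of readings is no easier to interpret.
- **Nothing decisive rests on Q9.** Correct. A reader might suppose the effectiveness conclusion is at risk; it is not. The protocol also does not map Q9 to its listed variable on recorded medication errors.
- **Mixing the versions is not planned.** Routing is separate, Section 9.7 stratifies by specialty, and Table 4 is a template whose final form is left to the SAP, which is not at hand. So it would be wrong to say that the plan combines them. The risk remains: both items carry the number Q9, the template has overall rows, and it names no separate row for pharmacists.

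The checks described in the protocol would not necessarily find the fault. Back-translation tests fidelity to the English and would reproduce it. Section 9.4 reports testing among 6 HCPs without saying whether any was a pharmacist.

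**Conclusion.** The point holds as a wording defect with descriptive consequences. Limb 1 of dispenser Q9 runs against both guides and against prescriber Q9, and limb 2 can be read in two directions. Pharmacists' answers are an uninterpretable mix and should not be presented as a count or rate of unclear prescriptions.

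The likely direction is understatement, since queries raised by pharmacists drop out on both literal readings and returns drop out on one. This assumes that prescribers query pharmacists less often than pharmacists query prescribers, which is plausible but not stated in the protocol. The size cannot be given: the protocol states no rate of clarification contacts, no split of readings, and no number of pharmacists per wave.

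It is worth correcting because the change is small and affects what is measured. It does not bear on the success factors.

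**What to change.** 1. For any wave not yet fielded, reword dispenser Q9 along these lines: *How many prescriptions for Suliqua have you queried with, or returned for clarification to, the prescriber in the last 3 months?* On the Section 6 milestones, Wave 3 (planned start 1 June 2021, if held) can carry it. Wave 2 collection was planned to start on 1 January 2020, before the amendment date of 24 February 2020 in the document history, so the change may come too late there.
2. Tabulate dispenser Q9 separately from prescriber Q9, under its own label and with no combined overall row, weighted or unweighted.
3. Report answers collected under the present wording as they stand, with a note on the ambiguity. Do not interpret them as a rate of unclear prescriptions.

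**Cost:** one sentence in the questionnaire and an update of each translation. Pharmacist Q9 answers from earlier waves cannot be pooled with those collected after the change.

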Annex 3 Patient/caregiver survey questionnaire

**SURVEY TO EVALUATE THE KNOWLEDGE AND UNDERSTANDING OF THE KEY
SAFETY MESSAGES IN THE HEALTHCARE PROFESSIONAL GUIDE AND THE
PATIENT GUIDE FOR SULIQUA**

- Patient / Caregiver questionnaire -

SCREENER

S1. Do you - or the person you take care of - work for any pharmaceutical company or advertising/research agency? Please select one answer

1	Yes	()
2	No	()

Data: single punch
If S1=1 then THANK&CLOSE

S2. Are you - or the person you take care of - treated with Suliqua for diabetes? Please select one answer

1	Yes	()
2	No	()

Data: single punch
If S2=2 then THANK&CLOSE

S3. How long have you - or has the person you take care of - been treated with Suliqua? Please select one answer

1	Less than 3 months	()
2	From 3 to 6 months	()
3	From 7 to 12 months	()
4	More than 12 months	()

Data: single punch

S4. What kind of pen are you - or is the person you take care of - using? Please select one answer

1	Peach (Suliqua 10-40)	()
2	Green (Suliqua 30-60)	()
3	I do not know	()

Data: single punch

S5. What is your gender/ what is the gender of the person you take care of? Please select one answer

1	Female	()
2	Male	()

Data: single punch

S6. What is your age/ what is the age of the person you take care of? Please select one answer

1	< 30 years old	()
2	31- 40 years old	()
3	41- 50 years old	()
4	51- 60 years old	()
5	61- 70 years old	()
6	71-80 years old	()
7	>80 years old	()

Data: single punch

QUESTIONNAIRE

Q1. Which of the following categories of doctors do you – or does the person you take care of - see for the management of diabetes? You can select more than one answer.

1	General practice (GP) / family physician	()
2	Endocrinologist	()
3	Gastroenterologist	()
4	Diabetologist	()
5	Geriatrician	()
6	Internist /(BE, UK): Internal medicine	()
7	Diabetes specialist nurse	()
8	Other	()

Data: multiple punch

Q2. Who has trained you - or the person you take care of - on the use of Suliqua? You can select more than one answer.

1	General practitioner (GP) / family physician	()
2	Another physician, please select the specialty in the following list:	()
3	Nurse	()
4	Pharmacist	()
5	No one	()

Data: multiple punch

List: Endocrinologist, gastroenterologist, internist, geriatrician, diabetes care clinic physician

Q3. According to your knowledge, which of the following statements are true and which are false?
 Please select one answer per row.

		TRUE	FALSE
1	The dose pointer of the pen shows the number of dose steps to be injected	()	()
2	1 dose step of Suliqua contains 1 unit of insulin glargine 100U/ml plus a corresponding amount of lixisenatide	()	()
3	Even when the needle is changed, the pen should not be used by another person	()	()
4	You cannot use a syringe to withdraw Suliqua from a pre-filled pen	()	()
5	It is important to closely monitor your blood sugar level when starting Suliqua	()	()
6	One dose step of Suliqua only states the amount of lixisenatide	()	()

Data: single punch per row

Answer: Option 6 is false.

Q4. According to your knowledge, which of the following statements are true and which are false?
 Please select one answer per row.

		TRUE	FALSE
1	The prescription should mention which pre -filled pen you should use	()	()
2	The Suliqua (10-40) pen allows a daily injection of doses between 10 and 40 dose steps	()	()
3	The Suliqua (30-60) pen allows a daily injection of doses between 30 and 60 dose steps	()	()
4	If my total daily dose is more than 60 dose steps, then I should not use any of the Suliqua pens	()	()

Data: single punch per row

If S4=1 then skip item 3

If S4=2 then skip item 2

If S4= 3 then keep item 2 and item 3

Answer: All is true

Q5. Have you - or has the person you take care of - received the Suliqua Patient Guide from your physician or pharmacist? Please select one answer

Yes No

Data: single punch

Q6. Have you - or has the person you take care of - read the following educational materials (EM) related to Suliqua before using Suliqua? Please select one answer per row.

1	Suliqua Patient Guide (information that you may have received from your physician or pharmacist)	 Yes  No
2	Patient Information Leaflet (information available in each pack of Suliqua pre-filled pen)	 Yes  No

Data: single punch per row

If Q5=2 then skip item 1

Q7. Where would you - or the person you take care of - look for additional information if you have difficulties in understanding the prescription or use of the Suliqua pen ? You can select more than one answer.

	Prescription/ missing information	
1	Ask a physician	()
2	Ask a pharmacist	()
3	Ask a nurse	()
4	Read the Information Leaflet from the Suliqua package	()
5	Read the Suliqua Patient Guide	()
6	Read on the web	()

Data: multiple punch
If Q5=2 then skip item 5

Answer: all is true

Note :

Blue is for data and will not appear in questionnaire

Green is for internal use and will not appear in questionnaire

Black will be in questionnaire

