9.2.4 Modalities of recruitment

9.2.4.1 HCP selection

HCPs will be identified from OneKey lists. A random stratified sampling method will be applied. As a first step, all lists will be merged, and then the eligible HCPs will be divided into homogeneous

groups, called strata, which are mutually exclusive (an HCP can only belong to one stratum). This stratification will be based on the following criteria:

Number of strata formed = number of countries * number of specialties

In order to fill-in each stratum of the sample survey from the IQVIA OneKey reference files, an independent sample will be selected per stratum through a simple random sampling without replacement.

In each specific stratum, HCPs will be contacted according to the order of draw in this stratum. If an HCP does not want to participate in the survey, the next one in order of draw will be contacted, and so on until the required number of HCPs is met. If the target for a stratum is not achieved after the end of the initial list, an additional randomly sampled list will be prepared, and the HCPs contacted until the goal is reached or no names are left in that stratum. If the complete list of the IQVIA OneKey reference files has been exhausted in any particular stratum, a strategy will be determined to adjust the sample size within stratum with associated weighting.

In web surveys, the number of HCPs to be contacted for reaching the required number of HCPs with analysable questionnaires is usually around ten times more than the expected final number.

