9.2.4.2 Patient selection

Only HCPs (physicians) prescribing SULIQUA will be involved in patient recruitment. An invitation letter to participate in the study will be randomly given to patients treated with SULIQUA at physician offices. As in the case of HCPs, a patient can only participate in one wave of the survey. There will be no limit on the number of patients recruited per HCP. Patients' data will be anonymous when presented to the MAH.

The prescription of therapies is the sole responsibility of the patient's physician.

The patients who will be enrolled in the study, will be selected among the patients for whom the physician has decided to prescribe SULIQUA independently from study entry.

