9.3.2 Variables collected through the patient questionnaire

Patient related variables include:

- Patients characteristics (age, gender, length of SULIQUA treatment)
- Treating physician (GP, endocrinologist/diabetologist, internist, gastroenterologist, geriatrist)
- Patient knowledge about SULIQUA pre-filled pen guide for patient (yes/no)
- Patient knowledge about SULIQUA pre-filled pen conditions of use (features and appropriate utilization of SULIQUA pre-filled pen, close blood sugar levels monitoring after initiation, safety information)

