9.7 DATA ANALYSIS

The statistical analyses will be described and further detailed into a Statistical Analysis Plan (SAP). The described analysis below might be revised, and adjustments might occur. The final SAP version will include (empty) table shells to be populated for the clinical study report (CSR).

General considerations:

The statistical analysis will be conducted using the SAS[®] software V9.4 on Windows[™] (SAS Institute, North Carolina, US).

Continuous variables will be described by their number (of valid cases, of missing values), mean, standard deviation, median, Q1, Q3, minimum and maximum. Categorical variables will be described as the total number and relative percentage per category. Confidence intervals of 95% will be evaluated, when relevant. The number of missing data will be indicated. Since, missing values are expected to be few and distributed at random, no replacement or imputation will be performed. Missing values will not be considered in the denominators for proportions.

For HCP questionnaire measures, results will be stratified by country and physician's specialty. For patient questionnaire measures, results will be stratified by country and treating physician's specialty. In tables "Overall - unweighted" columns and lines will show the results observed on the sample while "Overall weighted" columns and rows will show the results weighted according to the distribution of HCPs in the general population by country and specialty, respectively.

Two interim and 1 final analysis corresponding to 3 waves of survey will be performed according to timelines (Section 6) in selected European countries.

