9.7.1 Primary analysis

Distribution of all possible answers

As some questions may have multiple choices or be opened fields, the proportion of HCPs/patients having provided each possible answer will be described (Table 4).

Table 4: Mock table: Distribution of HCPs/patients answers to Question XX by country and physician specialty

Specialty	Answer	Country			Overall unweighted n(%)	Overall weighted * %
		Country 1 (N=XX)	Country 2 (N=XX)	...		
GP (N=XX)	Answer 1	xx (xx.xx)	xx (xx xx)	xx (xx xx)	xx (xx xx)	xx xx
	Answer 2	xx (xx.xx)	xx (xx xx)	xx (xx xx)	xx (xx xx)	xx xx
	...	xx (xx.xx)	xx (xx xx)	xx (xx xx)	xx (xx xx)	xx xx
	Missing	xx	xx	xx	xx	-
Endocrinologist (N=XX)	...	xx (xx.xx)	xx (xx xx)	xx (xx xx)	xx (xx xx)	xx xx
Internist (N=XX)	...	xx (xx.xx)	xx (xx xx)	xx (xx xx)	xx (xx xx)	xx xx
Gastroenterologist (N=XX)	...	xx (xx.xx)	xx (xx xx)	xx (xx xx)	xx (xx xx)	xx xx
Other (N=XX)	...	xx (xx.xx)	xx (xx xx)	xx (xx xx)	xx (xx xx)	xx xx
Overall unweighted (N=XX)	Answer 1	xx (xx.xx)	xx (xx xx)	xx (xx xx)	xx (xx xx)	xx xx
	Answer 2	xx (xx.xx)	xx (xx xx)	xx (xx xx)	xx (xx xx)	xx xx
	...	xx (xx.xx)	xx (xx xx)	xx (xx xx)	xx (xx xx)	xx xx
	Missing	xx	xx	xx	xx	-
Overall weighted	Answer 1	xx xx	xx xx	xx xx	xx xx	xx xx
	Answer 2	xx xx	xx xx	xx xx	xx xx	xx xx
	...	xx xx	xx xx	xx xx	xx xx	xx xx

* According to the distribution of HCPs in the general population by country and specialty, respectively.

Note: This template might be modified, final table shells will be presented in the statistical analysis plan (SAP).

Definition of success

Three success factors for professionals treating patients with SULIQUA will be defined:

1. Proportion of HCPs receiving the EMs (Question Q1 of HCP questionnaire).
2. Proportion of HCPs sufficiently understanding the key messages, i.e. providing at least 75% of correct answers (Questions Q3-Q4, Q7 of HCP questionnaire; at least 11 correct or consistent answers out of 14 sub-questions).
3. Proportion of HCPs adequately implementing the EMs, i.e. providing at least 75% of answers that are correct or consistent with appropriate use of the EMs (Questions Q2a-b, Q5-Q6 of HCP questionnaire; at least 12 correct or consistent answers out of 15 sub-questions).

Three success factors for patients/caregivers will be as follows:

1. Proportion of patients/caregivers receiving the EM (Question Q5 of Patient/Caregiver questionnaire).

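### Patient results are broken down by treating physician's specialty, but the only questionnaire item that supplies it allows several answers and never identifies the prescriber

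*Protocol*

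**What the plan says.** - **Stratification.** Section 9.7 states: "For patient questionnaire measures, results will be stratified by country and treating physician's specialty". The same section defines the overall weighted columns and rows as "results weighted according to the distribution of HCPs in the general population by country and specialty, respectively".
- **Table layout.** Mock Table 4 in section 9.7.1 is titled "Distribution of HCPs/patients answers to Question XX by country and physician specialty". Each specialty block has its own N, and unweighted and weighted overall lines follow.
- **Profiling.** Section 9.7.1 also describes patients with inappropriate answers by, among other things, the treating physician's specialty.
- **Source of the variable.** Section 9.3.2 lists it among the patient-questionnaire variables: "Treating physician (GP, endocrinologist/diabetologist, internist, gastroenterologist, geriatrist". Section 9.6.3.2 repeats the list.
- **The item itself.** Annex 3 Q1 asks which categories of doctors the patient would "see for the management of diabetes? You can select more than one answer". Its data note says multiple punch. The eight options list endocrinologist and diabetologist separately and include a diabetes specialist nurse and an open 'other' category.
- **The only other item naming specialties.** Annex 3 Q2 asks: "Who has trained you - or the person you take care of - on the use of Suliqua? You can select more than one answer".
- **The HCP side, for contrast.** Section 9.2.4.1 divides HCPs into "groups, called strata, which are mutually exclusive (an HCP can only belong to one stratum". Annex 2 item D2a records one main specialty as a single punch.
- **Recruitment.** Section 9.2.4.2: "Only HCPs (physicians) prescribing SULIQUA will be involved in patient recruitment".

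**The concern.** A table with one N per specialty and a weighted total needs each respondent in exactly one cell. The HCP side of the protocol meets that condition; the patient side does not. A patient who sees both a GP and an endocrinologist for diabetes can tick both in Q1, and nothing else in the questionnaire shows which of them prescribed SULIQUA or mainly manages the treatment.

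Three outputs are at stake:
- **By-specialty rows.** The same answers appear in two or more rows, which pulls the rows towards each other and makes their Ns add to more than the sample.
- **Specialty-weighted patient totals.** A patient in two strata has no single weight, so the total depends on an assignment rule that Q1 cannot justify.
- **The profile of patients with inappropriate answers.** It uses the same variable and inherits the same ambiguity.

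**Working it through.** **1. The plan's own figure.** Section 9.5.1 gives n = P(1−P)z²/e². With P = 0.5, z = 1.96 and e = 0.08, n = 0.25 × 1.96² / 0.08² = 150.06, so the stated 150 patients per wave is reproduced. The point here does not change that number.

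**2. Tracing the variable.** Section 9.7 needs one specialty per patient. Section 9.3.2 says that the patient questionnaire supplies it. Annex 3 has two candidate items:

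| Item | What it asks | Answers allowed | Identifies the prescriber? |
|---|---|---|---|
| Q1 | doctors seen for diabetes | several | no |
| Q2 | who gave training on SULIQUA | several | no |

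Neither yields one specialty per patient.

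**3. Size of the overlap.** The documents give no rate of shared care, so the share s of patients whose ticks fall in two different strata is an assumption. The sum of the specialty Ns is 150 × (1 + s):

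| s (assumed) | Sum of specialty Ns |
|---|---|
| 20% | 150 × 1.2 = 180 |
| 40% | 150 × 1.4 = 210 |
| 60% | 150 × 1.6 = 240 |

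A patient who ticks only endocrinologist and diabetologist does not count towards s, because section 9.3.2 combines the two.

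**4. Does the assignment rule matter for a weighted total?** This is an illustration in which every input is assumed. Take two specialties and 150 patients. Let 30% (45) tick both and split the rest equally (52.5 each). Let success be 70% in GP-only patients, 85% in endocrinologist-only patients and 90% in those ticking both, with a GP weight of 0.8.

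- GP row including dual patients: (52.5 × 0.70 + 45 × 0.90) / 97.5 = 77.25 / 97.5 = 79.2%.
- Endocrinologist row including dual patients: (52.5 × 0.85 + 45 × 0.90) / 97.5 = 85.125 / 97.5 = 87.3%.
- Dual patients assigned to GP: 0.8 × 79.2% + 0.2 × 85% = 80.4%.
- Dual patients assigned to endocrinologist: 0.8 × 70% + 0.2 × 87.3% = 73.5%.
- Dual patients counted in both: 0.8 × 79.2% + 0.2 × 87.3% = 80.8%.
- Unweighted, under any rule: (36.75 + 44.625 + 40.5) / 150 = 81.25%.

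With 10% ticking both, the three weighted figures are 75.9%, 73.2% and 76.1%. With 50% they are 83.7%, 73.7% and 84.3%. The weighted total moves with the rule; the unweighted one does not.

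**The case against.** Much can be said for the plan.

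- **The analysis is descriptive, and detail is deferred.** Section 9.7 leaves details and final table shells to the SAP, and Table 4 is marked as modifiable. Overlapping rows are ordinary for multiple-response data: a row for patients who see a GP is well defined even if some also see an endocrinologist. This stands for simple rows. It does not rescue a weighted total, and no SAP rule can supply the prescriber when Q1 did not record it.
- **The category differences are small.** Combining endocrinologist with diabetologist is a recode, and Table 4 already has an 'other' block. This stands; those differences are not the point.
- **Weighting of patients is not stated outright.** Section 9.5.2 requires weighting back for the HCP sample and gives only a pragmatic split for patients. Patient weighting is read from the general sentence in section 9.7 and the shared title of Table 4. That reading is fair, but it is an inference.
- **The recruiter's specialty is not excluded.** Section 9.7.2 counts HCPs with at least one submitted patient questionnaire, and Annex 2 pays per completed one, so some link to the recruiter is implied. The protocol still does not define the stratum that way.

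A reader might infer that the effectiveness verdict itself is unsafe, since the illustration crosses 80%. The documents do not support that. Section 9.7.1 sets the criterion on three patient proportions without naming specialty or weighted figures, and the illustration's inputs are invented. A reader might also infer that specialty differences are meant to steer follow-up. Section 9.7.1 links subsequent action to evaluating HCPs and patients separately, not to comparing specialties.

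**Conclusion.** The mismatch holds. The protocol stratifies and profiles patients by a specialty that its fixed questionnaire does not record uniquely, and on a fair reading of section 9.7 and Table 4 it also weights by it. The effect is confined to the by-specialty, specialty-weighted and profile results for patients. Unweighted overall results, country-only results and the sample size are untouched.

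The mismatch itself can be read directly from the documents. Its practical size cannot, because the share of patients ticking more than one stratum is unknown; the totals of 180, 210 and 240 rest on assumed shares. The change is worth making because it is cheap and because the missing information cannot be recovered at the analysis stage from Q1 alone.

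**What to change.** 1. In sections 9.3.2 and 9.7, define the patient's specialty stratum as the specialty of the recruiting physician. Only prescribing physicians recruit, and section 9.1 identifies HCPs by specialty from the OneKey lists. Carry the stratum as a country-and-specialty code on the patient kit or web link, without physician identity. Use it for stratification, any weighting and profiling.
2. Keep Q1 as a descriptive multiple-response item.
3. If kits and links cannot be coded, add one single-answer item on which doctor prescribed SULIQUA, using the section 9.3.2 categories.
4. For Wave 1 and Wave 2 patients already surveyed, use the recruiter's specialty only if kits or links were logged to recruiters. Otherwise report Q1 for them as overlapping rows, without specialty-weighted patient totals. Both waves are concerned: section 6 plans their collection from 01 September 2019 and 01 January 2020, and the amendment is dated 24 February 2020 in the document history.

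**Cost.** A printed or embedded code, or one extra question, and short wording changes; no extra participants. The stratum may be defined differently for earlier and later respondents, which should be stated in the report. Small country-by-specialty cells need checking against the Abstract's promise that patient data are anonymous to the research organisation and the marketing authorisation holder.
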